[Part 2 of 2 of the document. The other parts are not shown.]

Considering anti-glycan autoantibodies recognizing Gd-IgA1 are implicated in the pathogenesis of IgA nephropathy, exposure to the GalNAc moiety of cemdisiran may pose a theoretical risk of stimulating the production of pathogenic autoantibodies and immune complexes in patients with IgA nephropathy. This could presumably occur when antidrug antibodies (ADAs) to cemdisiran's triantennary GalNAc (Tri-GalNAc) cross-react with Gd-IgA1. The risk of developing these cross-reactive antibodies is likely low. This is based on the low incidence of ADA to cemdisiran in study ALN-CC5-001 (see Section 1.2) and the distinct difference in structure of the O-GalNAc moieties on a Gd-IgA1 glycoprotein and the Tri-GalNAc moiety in cemdisiran. This low risk is further mitigated by excluding patients with confirmed pre-existing IgG/IgM/IgA ADAs to total drug and real time monitoring for development of de novo IgG/IgM/IgA ADAs after dosing with cemdisiran. Patients with confirmed de novo ADAs will be discontinued from study drug but will continue to be monitored until EOS visit and subsequent safety follow up. Patients who develop positive ADA will be followed until ADA titers return to baseline. Additional ADA samples will also be collected if any clinical evidence of progression of IgAN disease and/or relevant safety findings.

Detailed information about the known and expected benefits and risks of cemdisiran and additional information on the clinical and nonclinical data may be found in the current version of the IB.

Cumulatively, clinical data regarding the role of complement pathways in IgAN progression, robust nonclinical and clinical data with cemdisiran (see IB for more information), and prior and ongoing clinical experience with other RNAi therapeutics in humans suggest cemdisiran will have a favorable risk profile in the intended population and supports the initial clinical development of cemdisiran in IgAN. In addition, cemdisiran may address the unmet medical need for the first efficacious and disease-specific treatment for patients with IgAN.

## 2. OBJECTIVES AND ENDPOINTS

Objectives	Endpoints
Primary	

To evaluate the effect of cemdisiran on proteinuria in adult patients with immunoglobulin A nephropathy (IgAN)

	

Percent change from baseline in 24-hour proteinuria (g/24-hours) at Week 32

Secondary	

Percent of patients with partial clinical remission (urine protein [UP] <1.0 g/24-hours) at Week 32

Percent of patients with >50% reduction in 24-hour proteinuria at Week 32

Change from baseline in urine protein/creatinine ratio (UPCR; in g/g) as measured in 24-hour urine at Week 32

Change from baseline in UPCR as measured in a spot urine at Week 32

Change from baseline in hematuria at Week 32 (red blood cells per high powered field [RBC/hpf])

Frequency of adverse events (AEs)

Exploratory	

To evaluate the effect of cemdisiran on renal function parameters

To evaluate the pharmacodynamic (PD) effect of cemdisiran in adult patients with IgAN

To characterize the pharmacokinetics (PK) of cemdisiran and relevant metabolites in plasma and urine in adult patients with IgAN

To evaluate the effect of cemdisiran on serum and urine markers of complement activation, renal damage and inflammation

To assess the incidence of antidrug antibodies (ADA)

 

Change from baseline in estimated glomerular filtration rate (eGFR) at Week 32

The slope of eGFR computed for the first 32 weeks using all assessments during the period

The slope of eGFR computed for the entire study period including the open label extension using all assessments during the study.

Change from baseline in creatinine clearance at Week 32

Percent of patients in full clinical remission (Urine Protein [UP] <0.3 g/24-hours) at Week 32

	

• Change from baseline in 24-hour albuminuria at Week 32

• Change from baseline in the urine albumin/creatinine ratio (UACR) as measured in 24-hour urine at Week 32

• Change from baseline in C5 level over the course of the study

• Change from baseline in complement activity (Complement Alternative Pathway [CAP] and Complement Classical Pathway [CCP]) over the course of the study

• Evaluation of area under the curve (AUC), maximum plasma concentration (<math>C_{max}</math>), time to maximum plasma concentration (<math>T_{max}</math>), terminal half-life (<math>t_{1/2}</math>), clearance (CL/F), volume of distribution (V/F), cumulative amount excreted unchanged in urine (Ae) and percent of dose excreted in the urine (fe) of cemdisiran (25-mer) and 23-mer

• Evaluation of AUC, <math>C_{max}</math>, <math>T_{max}</math>, <math>t_{1/2}</math>, CL/F, V/F, Ae and fe of 22-mer AS(N-1)3'

• Change from baseline in levels of renal damage, complement activation and inflammation markers over the course of the study

• Incidence of antidrug antibodies (ADA)

--	-----------------------------------------------------------------------------------------------------------------------------------------------------------------------------------------------------------------------------------------------------------------------------------------------------------------------------------------------------------------------------------------------------------------------------------------------------------------------------------------------------------------------------------------------------------------------------------------------------------------------------------------------------------------------------------------------------------------------------------------------------------------------------------------------------------------------------------------------------------------------------------------------------------------------------------------------------------------------------------------------------------------------------------------------------------------------------------------------------------------------------------------------------------------------------------------------------------

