#### 5.2.2. Dose and Administration

Patients will be administered cemdisiran (600 mg) or placebo (at the same volume as the active drug) as an SC injection once every 4 weeks in combination with standard of care in the 32-week treatment phase. During the 52-week OLE phase, patients will be administered cemdisiran at a dose of 600 mg every 4 weeks in combination with standard of care.

Study drug injections will be administered under the supervision of the Investigator or healthcare professional. At-home dosing may be administered by a healthcare professional. The injection site may be marked and mapped for later observation. The preferred site of injection is the abdomen. Optional additional sites are the upper arms and thighs. If a local reaction around the injection site occurs, photographs may be obtained, if permitted. Detailed instructions for study drug administration are found in the Pharmacy Manual.

To maintain the blind during the treatment period, the syringes are to be masked prior to study drug withdrawal. A full description of the blinding procedure is included in the Pharmacy Manual.

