### **6.6. Pharmacokinetic Assessments**

Blood samples and urine samples will be collected for assessment of cemdisiran PK parameters and possible metabolite analysis at the time points in the Schedule of Assessments. A detailed schedule of time points for the collection of blood samples and urine samples for PK analysis is in [Table 3](#).

The concentration of cemdisiran will be determined using a validated assay. Details regarding sample volumes to be collected, and the processing, shipping, and analysis of the samples will be provided in the Laboratory Manual.

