#### 7.2.7. Pharmacokinetic Analysis

Pharmacokinetic analyses will be conducted using noncompartmental methods. Pharmacokinetic parameters include, but will not be limited to: AUC,  $C_{max}$ ,  $T_{max}$ ,  $t_{1/2}$ , CL/F, V/F, cumulative amount excreted unchanged in urine (Ae), and percent of dose excreted (fe) in the urine of cemdisiran (25-mer) and 23-mer.

Other parameters may be calculated, if deemed necessary. Summary statistics and figures will be presented. Inferential statistics may be generated when deemed necessary.

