classical pathway (CCP) activity by Day 14 and 90.2% and 91.4% reduction in CAP and CCP activities, respectively, by Day 56. Single and multiple biweekly doses of 600 mg were well-tolerated with an acceptable safety profile in healthy volunteers in Study ALN-CC5-001A. In this initial study, the cemdisiran dose of 600 mg that was safe and well-tolerated was chosen for evaluation. This dose will yield robust C5 silencing and will have maximal opportunity to produce a meaningful clinical effect in patients with IgAN. Since the relationship between C5 levels and complement activity is non-linear, with small C5 fluctuations resulting in a larger increase in complement activity, a monthly dose regimen was selected to maintain a constant level of C5 silencing. Additionally, a more consistent effect of cemdisiran on C5 protein and CCP level is predicted after monthly dosing when compared to quarterly dosing based on a modeling approach.

During the extension treatment phase, patients treated with both cemdisiran and placebo will have the option to receive a 600 mg dose of cemdisiran every four weeks for an additional 52 weeks.

IgAN can result in progressive renal impairment; however, patients with severe renal impairment (eGFR<30 mL/min/1.73 m^2) who may have sustained irreversible damage to the kidney are not eligible for participation in this trial. As the kidney is not the major elimination pathway for cemdisiran and based on available nonclinical and clinical data obtained with cemdisiran (with 10.6 to 31.6% of the cemdisiran dose recovered in a 24-hour urine collection in the ALN-CC5-001 study), it is expected that moderate renal impairment (eGFR<60 mL/min/1.73 m^2) will not affect the PK of cemdisiran to the extent that a dose adjustment would be required.

Therefore, patients with moderate renal impairment are eligible for study enrollment. More information on urine PK can be found in the IB.

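### CL/F and V/F are listed as endpoints for the 22-mer metabolite, which is never dosed; the values would carry an unknown conversion fraction that the label does not disclose

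*Protocol*

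**What the plan says.** Section 2 of the protocol sets an exploratory PK objective: "To characterize the pharmacokinetics (PK) of cemdisiran and relevant metabolites in plasma and urine in adult patients with IgAN". Two endpoint bullets serve it. One covers cemdisiran (25-mer) and the 23-mer. The other covers a separate analyte and asks for AUC, Cmax, Tmax, terminal half-life and "CL/F, V/F, Ae and fe of 22-mer AS(N-1)3". The first of these bullets spells CL/F and V/F out as clearance and volume of distribution, and nothing qualifies those terms for an analyte that is not given.

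On dosing, Section 5.2.2 says: "Patients will be administered cemdisiran (600 mg) or placebo (at the same volume as the active drug) as an SC injection". On method, Section 7.2.7 says: "Pharmacokinetic analyses will be conducted using noncompartmental methods". That section names the 25-mer and 23-mer in an expressly open-ended list. Section 6.6 provides blood and urine samples for cemdisiran and for "possible metabolite analysis at the time points in the Schedule of Assessments".

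The one dose-fraction figure at hand is in Section 1.4 (Amendment 1 text): "with 10.6 to 31.6% of the cemdisiran dose recovered in a 24-hour urine collection". It describes recovery of the cemdisiran dose in urine, not conversion to the 22-mer.

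**The concern.** In noncompartmental analysis, CL/F and V/F are formed from the dose and the exposure to the analyte. That works when the analyte is what was injected: the only unresolved quantity is bioavailability, and the /F says so. For a metabolite, the amount entering the circulation is the injected dose multiplied by bioavailability and by the fraction converted. The second factor is unknown here, and nothing in the parameter name reveals it.

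If the endpoint is carried out as written, a table will show a clearance and a volume for the 22-mer that are neither. A reader could compare them with the parent's values, or with another study's, as if they described how the 22-mer is eliminated and distributed. A difference could equally come from a difference in formation. Because the protocol itself names these parameters as endpoints, later analysis detail cannot make the true values identifiable; it can only relabel or omit them.

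**Working it through.** The plan gives no figure of its own to reproduce. The check is whether the listed parameters can be identified from this design.

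**Inputs from the protocol**

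- Substance given: cemdisiran 600 mg subcutaneously (Section 5.2.2). No arm doses the 22-mer.
- Method: noncompartmental (Section 7.2.7).
- Fraction converted to the 22-mer: not given. The 10.6 to 31.6% in Section 1.4 is a different quantity.
- Status of the 22-mer: not stated outright. It is inferred from the metabolite objective, the separate bullet and the N-1 name.

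**Formulas** (linear kinetics; dose and metabolite in the same molar units)

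- Metabolite exposure after a parent dose: AUC_m = F x fm x Dose / CLm
- Hence Dose / AUC_m = CLm / (F x fm)
- If the terminal slope lambda_z is the metabolite's own elimination rate, Dose / (AUC_m x lambda_z) = Vm / (F x fm)

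**Illustration.** All values other than the 600 are assumed, and 600 is used as a number only: F = 0.8, CLm = 10 L/h, Vm = 80 L. Then lambda_z = 10/80 = 0.125 per h, the half-life is 0.693/0.125 = 5.55 h (5.545 before rounding), and CLm/F = 10/0.8 = 12.5 L/h.

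| fm | AUC_m = 0.8 x fm x 600/10 | Dose/AUC_m (L/h) | Multiple of CLm/F | Dose/(AUC_m x 0.125) (L) |
|---|---|---|---|---|
| 0.05 | 2.4 | 250 | 20 | 2000 |
| 0.1 | 4.8 | 125 | 10 | 1000 |
| 0.25 | 12 | 50 | 4 | 400 |
| 0.5 | 24 | 25 | 2 | 200 |
| 1.0 | 48 | 12.5 | 1 | 100 |

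The metabolite's true clearance, volume and half-life are the same in every row. Only fm changes.

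**Could the plasma curve reveal fm?** No. The metabolite concentration depends on fm and Vm only through fm/Vm, and on CLm and Vm through CLm/Vm. Take (fm, CLm, Vm) = (0.1, 10, 80), (0.2, 20, 160) and (0.5, 50, 400). In each, fm/Vm = 0.00125 and CLm/Vm = 0.125. The simulated curves coincide (maximum relative difference below 1e-13), although true clearance differs fivefold. Urine does not close the gap: Ae over AUC for the same interval gives the renal part of metabolite clearance, not the total.

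**Why only at best for V/F.** Suppose the metabolite is eliminated faster than it is supplied: CLm = 80 L/h, Vm = 40 L, fm = 0.1, with a slowest upstream rate of 0.3 per h.

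- True elimination rate: 80/40 = 2.0 per h, half-life 0.35 h. Observed terminal half-life: 0.693/0.3 = 2.31 h.
- AUC_m = 0.8 x 0.1 x 600/80 = 0.6, so Dose/AUC_m = 1000 L/h, which still equals CLm/(F x fm) = 80/0.08.
- Dose/(AUC_m x lambda_z) = 1000/0.3 = 3333 L, against Vm/(F x fm) = 40/0.08 = 500 L.

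In that case V/F is not even the apparent volume with fm in the denominator.

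**The case against.** The best defence is that CL/F and V/F are apparent parameters by name. For an analyte that is not dosed, F can be read as the fraction of the dose reaching the circulation as that analyte, which is F x fm. A number can certainly be calculated. On this view all that is missing is a footnote, and such notes usually sit in a statistical or PK analysis plan. Part of this stands: an explicitly labelled apparent ratio is legitimate, and saying that nothing can be computed would be too strong. But the protocol does not give F that meaning, and its endpoint list spells the terms out as clearance and volume of distribution. A reader will take F as bioavailability.

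A second defence is that the 22-mer is never expressly called a metabolite. That is right, and the point rests on inference. The inference is firm, because no other stated PK objective would call for a separate analyte with that name.

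Several stronger readings are tempting, and the documents do not support them:

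- **That Section 7.2.7 contradicts Section 2 by omitting the 22-mer.** It ends with "percent of dose excreted (fe) in the urine of cemdisiran (25-mer) and 23-mer", but it says its list is not limiting and that other parameters may be calculated.
- **That fe for the 22-mer is wrong.** The protocol does not say it will be computed by mass, and on a molar basis it is sound.
- **That the PK objective concerns reduced renal function, so shifts with eGFR would be misread.** The objective is adult patients with IgAN, and Section 7.2.7 specifies no PK analysis by eGFR.
- **That the 23-mer should lose its CL/F and V/F too.** Its status is not defined.
- **That the values mainly reflect low formation.** Nothing shows whether fm is high or low.

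**Conclusion.** The point holds in a narrow form. As written, the endpoint would tabulate CLm/(F x fm) and, at best, Vm/(F x fm) under names that mean clearance and volume of distribution, and no analysis of these data can remove fm. The conclusion assumes that the 22-mer is a metabolite, that kinetics are linear and that fm is unknown.

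The size of the mislabelling cannot be stated. It is a factor of 1/fm, and the multiples of 1 to 20 above are illustrations over assumed fm values, not estimates.

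The consequence is minor. Two of eight parameters for one analyte are affected, in an exploratory endpoint that is summarized descriptively. The primary proteinuria analysis is untouched. AUC, Cmax, Tmax, Ae and fe for the 22-mer remain valid, and t1/2 can be reported as an observed terminal half-life.

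**What to change.** In Section 2, and wherever the same bullet is repeated (such as the synopsis endpoint table), do one of two things for the 22-mer:

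- delete CL/F and V/F; or
- keep them under the explicit labels CLm/(F x fm) and Vm/(F x fm), with a note that fm is not identifiable in this trial and that the second holds only if the terminal slope reflects metabolite elimination.

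Keep AUC, Cmax, Tmax, Ae and fe, and describe t1/2 as the observed terminal half-life. Add the molar metabolite-to-parent ratios of AUC and Cmax, which describe relative exposure without needing fm. Leave the 25-mer and 23-mer bullet as it is.

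The cost is a wording change. The ratios use the samples already planned and the concentrations needed for the parameters already listed, so there are no new visits, samples or assays.

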### 3. INVESTIGATIONAL PLAN

#### 3.1. Summary of Study Design

This is a multicenter, double-blind, placebo-controlled study comprised of three periods ([Figure 1](#)). The first period of the study is an observational 14-week run-in period during which patients' blood pressure, kidney function, degree of hematuria, and proteinuria will be measured. Patients will not receive study drug (cemdisiran or placebo) during this time. The standard of care is expected to remain unchanged during this run-in period. The second study period is a 36-week treatment period which will evaluate the efficacy and safety of SC cemdisiran compared to SC placebo in combination with standard of care in patients with IgAN and persistent proteinuria. The third period of the study is a 52-week optional open-label extension (OLE) period to further evaluate the long-term safety and clinical activity of cemdisiran. During the OLE, all patients (including those initially on placebo) will be treated with cemdisiran in combination with standard of care.

The study will include Screening of up to 90 days to determine eligibility of patients and to complete disease-related assessments. Patients will provide written informed consent and visit the study center approximately 2 weeks before starting the run-in period to complete the protocol screening assessments. Following successful screening, the 14-week run-in period will commence, during which patients' blood pressure, kidney function, degree of hematuria and proteinuria as well as treatment with standard of care will be documented by the Investigator. The standard of care is expected to remain unchanged during this run-in period. Patients whose proteinuria level remains  $\geq 1$  g/24-hours within 2 weeks of the end of the run-in period, and who meet blood pressure and eGFR criteria will be eligible to enroll in the 36-week treatment period. Upon confirmation of eligibility followed by vaccination against meningococcal infections, patients will be randomized at a 2:1 ratio to receive 600 mg of cemdisiran or placebo every 4 weeks in combination with standard of care. Approximately 30 patients are planned to be randomized in total, 20 in the cemdisiran arm and 10 in the placebo arm. Patients excluded before randomization will be replaced at Screening.

During the run-in period, patients will visit the study center 14, 8, and 2 weeks prior to randomization (Weeks 0, 6 and 12 of the run-in period). Patients will then return to the study center every 4 weeks after the start of study drug treatment period. The primary endpoint will be assessed at the end of treatment at Week 32.

At the end of treatment (Week 32), patients in the two treatment arms will enter the optional OLE period where they will receive cemdisiran at a dose of 600 mg every 4 weeks in combination with standard of care for 52 weeks. The first study drug administration of the OLE will be administered at Week 36. Patients will return to the study center at Week 40 and every 8 weeks thereafter during the OLE. Home visits, where locally feasible, may be arranged for cemdisiran administration in between 8-weekly study center visits (Weeks 44, 52, 60, 68 and 76), unless patients are required to visit the study center as judged necessary by the Investigator, or if home visits cannot be arranged. An end of treatment (EOT) visit will occur at Week 80 (OLE EOT) and an end of study (EOS) or early termination (ET) visit will be completed at Week 84 (OLE EOS/ET). For patients who complete the treatment period only who do not consent to continue to participate in the study in the OLE period, the EOS/ET visit will be at Week 36.

Patients will return to the clinical study center for safety follow-up visits approximately 13, 26, 39 and 52 weeks after the EOS/ET visit (regardless if EOS/ET visit is at Week 36 or Week 84), unless enrolled in another study with cemdisiran. Home visits, where locally feasible, may be arranged during safety follow-up at 13 and 39 weeks after the EOS/ET visit (regardless if EOS/ET visit is at Week 36 or Week 84).

Regular reviews of safety and tolerability data will be performed by an independent data monitoring committee (DMC) throughout the study with the primary purpose of protecting the safety of participating patients and the integrity of the study.

### **3.2. Duration of Treatment**

Subcutaneous doses of cemdisiran or matching placebo will be administered every 4 weeks over a period of 32 weeks during the treatment period and patients will receive 600 mg SC doses of cemdisiran for 52 weeks in the optional OLE.

### **3.3. Duration of Study**

The maximum estimated total time on study, inclusive of Screening (maximum of 90 days), run-in period (14 weeks), treatment period (36 weeks), optional OLE period (52 weeks) and safety follow-up (52 weeks), is approximately 36 months or 3.0 years.

#### **3.3.1. Definition of End of Study for an Individual Patient**

A patient is considered to have reached the end of the study if the patient has completed the EOS visit (Week 36 for those patients who do not consent to continue to participate in the study in the OLE period and Week 84 for patients who enter the OLE period). Upon study completion (regardless if EOS visit is at Week 36 or Week 84) patients will enter a safety follow-up period with visits scheduled at intervals of 13 weeks.

For patients withdrawing from the study after receiving one dose of cemdisiran at a minimum (ET), all efforts should be made to conduct the EOS/ET assessments. Patients should then be encouraged to enter the safety follow up period.

